## 9.3.2 Analysis of Key Secondary Variables

### 9.3.2.1 Definition of Variables

Sweat chloride (SwCl): the SwCl value for a given visit will be calculated as the mean of the non-missing sweat chloride measurements obtained on the left and right arms at that visit. If one of the two arm measurements at a time point is missing, the other will be used as the mean. A volume  $\geq 15 \mu\text{L}$  is required for an accurate determination of sweat chloride. Any results reported as having volume  $< 15 \mu\text{L}$  will be considered missing. Any sweat chloride values reported as  $< 10 \text{ mmol/L}$  or  $> 160 \text{ mmol/L}$  will be considered missing.

Cystic Fibrosis Questionnaire-Revised (CFQ-R): The CFQ-R is a validated CF-specific instrument that measures quality-of-life domains. This study utilizes three different versions of CFQ-R:

- CFQ-R for Children ages 12 and 13
- CFQ-R for Adolescents and Adults (subjects 14 years and older)
- CFQ-R for Parents/Caregivers (subjects 13 years and younger)

In all three versions, specific question belonging to a domain is scored 1, 2, 3, or 4. The CFQ-R domain score, e.g., physical domain score or respiratory domain score, is defined as a scaled score as follows:

Scaled score for a domain =  $100 \times (\text{mean (scores of all questions in the domain)} - 1)/3$ ,

where the score from a negatively phrased question is first reversed, i.e., reversed score =  $5 - \text{actual score}$ , so that 1 always represents the worst condition and 4 the best condition. The (scaled) domain score ranges from 0 (worst condition) to 100 (best condition). The scaled score for a specific domain will not be calculated if more than half of the questions in the domain have missing scores.

The (scaled) domain score from the CFQ-R for Children ages 12 and 13 and for Adolescent and Adults will be pooled for the analysis purpose.

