10.7.1 Blinding

All subjects (and their parents/caregivers/companions), site personnel (including the investigator, the site monitor, and the study team), and members of the Vertex study team will be blinded to the treatment codes.

Individuals who may be unblinded include only the following:

- Any site personnel for whom this information is important to ensure the safety of the subject in the event of a life-threatening medical emergency
- Any site personnel for whom this information is important to ensure the safety of the subject and her fetus in the event of a pregnancy
- Vertex Global Patient Safety (GPS) and Regulatory Affairs personnel to satisfy SAE processing and reporting regulations
- Vendor preparing the final (production) randomization list
- Vertex IWRS Manager
- Vertex Clinical Supply Chain
- IDMC
- Vendor preparing the unblinded analysis of safety data for review by the IDMC
- Bioanalytical contract research organization (CRO) analyzing PK samples and the Vertex Bioanalytical personnel who is not a member of the study team but reviews raw data from the Bioanalytical CRO. The Vertex Bioanalytical study team member will continue to be blinded.

Access to Spirometry and SwCl Results:

During the conduct of the study, the Vertex study team will not have access to the spirometry or SwCl results after the first dose of study drug in the Treatment Period.

Shortly before any planned efficacy analysis is conducted, the spirometry and SwCl data will be reviewed for data cleaning purposes by a biostatistician who does not have access to the treatment codes.

Individual SwCl test results will not be disclosed to the study sites with the exception of the screening values. Subjects and their parents/caregivers/companions should not be informed of study-related spirometry results until Vertex has determined that the study has completed (i.e., CSR finalization), regardless of whether the subject has prematurely discontinued treatment.

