11.4 Pharmacodynamics: Sweat Chloride

SwCl samples will be collected with an approved collection device. Each collection will occur before study drug dosing ([Section 9.6.1](#)). At each time point, 2 samples will be collected, 1 from each arm (left and right). Sweat samples will be sent to a central laboratory for testing and interpretation of results. Specific instructions for the collection, handling, processing, and shipping of SwCl samples to the central laboratory will be provided separately.

See [Section 10.7.1](#) for information about access to SwCl results.

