##### **9.3.1.2 Primary Analysis**

The primary analysis will be performed using a mixed-effects model for repeated measures (MMRM) with the absolute change from baseline at Day 15 and Week 4 as the dependent variable. The model will include treatment group, visit, and treatment-by-visit interaction as fixed effects, with continuous baseline ppFEV1, and age at screening (<18 versus ≥18 years of age) as covariates. The model will be estimated using restricted maximum likelihood. Denominator degrees of freedom for the *F*-test for fixed effects will be estimated using the Kenward-Roger approximation. An unstructured covariance structure will be used to model the within-subject errors. If the model estimation does not converge, a compound symmetry covariance structure will be used instead. Conditional on the observed data and covariates, missing data will be assumed to be missing at random; consequently, no imputation of missing data will be performed.

The primary result obtained from the model will be the estimated treatment difference at Week 4. The adjusted means with 2-sided 95% confidence intervals and 2-sided *P* values will be provided. Furthermore, the treatment difference at each post-baseline visit obtained from the model will also be provided.

The adjusted mean (with SE) obtained from the MMRM analysis at each post-baseline visit up to Week 4 will be plotted by treatment group.

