#### 9.3.2.2 Analysis Method

Absolute change in SwCl from baseline at Week 4:

Analysis of absolute change from baseline in sweat chloride will be based on an MMRM similar to the primary analysis of the primary efficacy variable. The model will include treatment, visit, and treatment-by-visit interaction as fixed effects with continuous baseline ppFEV1, and age at screening ( $< 18$  versus  $\geq 18$  years of age) as covariates.

Absolute change in CFQ-R respiratory domain score from baseline at Week 4:

Analysis of absolute change from baseline in CFQ-R respiratory domain score will be based on an MMRM similar to the primary analysis of the primary efficacy variable. The model will include treatment, visit, and treatment-by-visit interaction as fixed effects with continuous baseline ppFEV1, and age at screening ( $< 18$  versus  $\geq 18$  years of age) as covariates.

To assess the longitudinal profile of the efficacy and pharmacodynamic assessments with repeated measures up to Week 4, the LS mean (SE) of the within-treatment group change from baseline at each post-baseline visit along with the 95% CI will be estimated from the

corresponding MMRM. The LS mean (SE) of the treatment difference between VX-659/TEZ/IVA and TEZ/IVA at each post-baseline visit will be provided along with the corresponding 95% CI and *P* value. The LS mean (SE) at each visit will also be plotted by treatment group. In addition, the post-baseline raw values and the absolute change from baseline at each post-baseline visit up to Week 4 will be summarized descriptively (n, mean, SD, median, minimum, and maximum).

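### Does setting sweat chloride readings below 10 mmol/L to missing bias the first key secondary endpoint enough to need a different rule?

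*SAP*

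**What the plan says.** SAP 9.3.2.1 defines the visit value of sweat chloride as the average of the left-arm and right-arm readings, and has three rules for readings that are not used.

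- Volume: "Any results reported as having volume $< 15 \mu\text{L}$ will be considered missing". The SAP gives accuracy of the determination as the reason.
- Range: "Any sweat chloride values reported as $< 10 \text{ mmol/L}$ or $> 160 \text{ mmol/L}$ will be considered missing". No reason is given.
- One arm unusable: "If one of the two arm measurements at a time point is missing, the other will be used as the mean".

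On collection, Protocol 11.4 says "At each time point, 2 samples will be collected, 1 from each arm (left and right", and then "Sweat samples will be sent to a central laboratory for testing and interpretation of results". It gives no reportable range; detailed handling instructions are left to a separate document.

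For the model, SAP 9.3.2.2 says "Analysis of absolute change from baseline in sweat chloride will be based on an MMRM similar to the primary analysis of the primary efficacy variable". Its covariates are baseline ppFEV1 and age group; baseline sweat chloride is not among them. The primary analysis in SAP 9.3.1.2 states that "missing data will be assumed to be missing at random; consequently, no imputation of missing data will be performed". The endpoint is tested first among the key secondaries (SAP 9.3.2.3).

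**The concern.** The volume rule already deals with inadequate samples. The range rule therefore also removes a reading from an adequate sample because of its own value, and missingness that depends on the unobserved value is not missing at random. The drug under test is expected to lower sweat chloride, so genuine readings below 10 would fall almost entirely in the triple-combination group.

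There are two routes to a shift. If one arm reads 8 and the other 14, the visit value becomes 14 instead of 11. If neither arm is usable, the visit is lost and the model fills the gap from Day 15, which passes through the same filter. Both routes raise the triple-combination mean and understate the treatment difference. At stake are the estimate and confidence interval of the first key secondary endpoint.

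**Working it through.** **The plan's own figure.** The only power stated is for ppFEV1 (Protocol 12.1, SAP 7.2). With 50 × 0.95 = 47.5 per group, difference 5.0 and SD 7, the standard error is 7 × √(2/47.5) = 1.436. The noncentrality is 5.0/1.436 = 3.48 on 93 degrees of freedom, and power is 0.931. The stated 93% is reproduced. It does not involve sweat chloride, for which the documents give no mean, SD or power.

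**Assumed inputs for sweat chloride.** Baseline and control mean 90, SD 12. Triple-combination mean and SD as tabulated. Correlation 0.8 between visits and 0.5 with baseline. Two readings per visit, each with error SD 5. Every reading below 10 is taken as genuine, which is the least favourable case for the plan. In a large simulated sample, the rule was applied to each reading, the surviving readings were averaged, and the Week 4 mean change was estimated by maximum likelihood with unstructured covariance over Day 15 and Week 4.

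**Standard error in a trial of this size** (before covariate adjustment). The variance of change on triple combination is SD² + 12² − 2 × 0.5 × SD × 12 + 25, where 25 is the error variance of two two-reading averages (12.5 + 12.5). At SD 20 this is 400 + 144 − 240 + 25 = 329. For control it is 144 + 144 − 144 + 25 = 169. The standard error is √((329 + 169)/47.5) = 3.24. The same formula gives 2.84 at SD 15 and 3.06 at SD 18.

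Approximate 95% CI coverage is Φ(1.96 − r) − Φ(−1.96 − r), with r = shift/SE.

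| TC mean / SD | True difference | Shift toward zero | Shift as % of difference | SE | Coverage |
|---|---|---|---|---|---|
| 50 / 15 | −40.00 | 0.08 | 0.2 | 2.84 | 95.0% |
| 50 / 20 | −39.96 | 0.51 | 1.3 | 3.24 | 94.7% |
| 40 / 15 | −49.94 | 0.41 | 0.8 | 2.84 | 94.8% |
| 40 / 20 | −49.69 | 1.30 | 2.6 | 3.24 | 93.1% |
| 30 / 15 | −59.76 | 1.30 | 2.2 | 2.84 | 92.6% |
| 35 / 20 | −54.50 | 1.90 | 3.5 | 3.24 | 91.0% |
| 30 / 18 | −59.43 | 2.08 | 3.5 | 3.06 | 89.6% |

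At 60 / 15 the shift is 0.01. No simulated control reading fell below 10 or above 160.

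**Test decision.** The smallest ratio of shifted difference to standard error in the table is (39.96 − 0.51)/3.24 = 12.2, so significance is not in question. If the two groups had the same distribution, the filter would act equally on both, so type I error is not affected.

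**Cost of the alternative.** Suppose low readings are kept and some are artefacts spread evenly over 0 to 10, with average 5, at the same rate in both groups. A rate p lowers the control mean by p × (90 − 5) and the triple-combination mean by p × (m − 5), so the difference moves toward zero by p × (90 − m). At p = 1% that is 0.40, 0.50 and 0.60 mmol/L for m = 50, 40 and 30. The rule in the SAP discards these artefacts. The break-even rate is the shift divided by (90 − m), which is essentially the percentage column of the table. At 50 / 15, artefacts in 0.2% of readings make the current rule the better one; at 40 / 15, 0.8%; at 30 / 18, 3.5%.

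**Single events.** Losing one triple-combination visit of 7 mmol/L from 47.5 subjects with mean 40 moves that mean by (47.5 × 40 − 7)/46.5 − 40 = 0.71, or 0.92 with mean 50. Keeping one artefactual reading of 5 in a control subject whose other arm reads 90 gives 47.5 for the visit and moves the control mean by (90 − 47.5)/47.5 = 0.89. The two errors are of the same order and in the same direction. The one-arm case of 14 instead of 11 moves the mean by 3/47.5 = 0.06.

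**The case for a change.** The best case for acting is that the SAP explains its volume limit and not its range limit. A reader of the results could not tell how many readings were removed, from which group, or why. One question to the laboratory, a count table and a second run would be cheap. Two possible safeguards do not remove the shift: Day 15 data recover only part of it (at 40 / 20, from 1.56 on observed cases to 1.30 in the model), and blinded cleaning under Protocol 10.7.1, where "the spirometry and SwCl data will be reviewed for data cleaning purposes by a biostatistician who does not have access to the treatment codes", prevents selective handling only.

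The mechanism stands, and so does the direction if the lows are genuine. What does not follow is that the rule is wrong. A two-sided range placed directly after an accuracy rule, for samples tested and interpreted centrally, reads naturally as an assay validity range, though the text does not prove it. SAP 9.3.2.2 already reports n and the minimum of raw values at each post-baseline visit, so lost visits and values close to 10 would be visible, although single-arm exclusions would not. Parts of the SAP are blacked out, so the absence of a visible sensitivity analysis is not evidence that none is planned.

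A replacement rule would also bring difficulties. It would need a laboratory validity flag that no visible section describes. Keeping lows while still dropping values above 160 would treat the two limits differently without a reason. Leaving the main rule open until the laboratory replies is worse, for a hierarchically tested endpoint, than one fixed rule.

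**Conclusion.** The plan can stand. The range rule makes missingness depend on the outcome only if readings below 10 from adequate samples are genuine, and the documents do not settle that. Even on that assumption, the Week 4 difference is understated by about 0 to 1.3 mmol/L for triple-combination means of 40 to 60, and by about 2 mmol/L only for means of 30 to 35 with SD 18 to 20. This is under 4% of the difference throughout. Coverage stays at about 93% or better for means of 40 and above, and falls to about 90 to 91% only in the extreme cases. The shift works against the sponsor, leaves type I error and the primary endpoint untouched, and does not change the test decision.

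These sizes rest on assumed means, SDs, correlations and normal-type lower tails. Because retained artefacts cost a similar amount, neither rule is better in every case. Keeping the single prespecified rule is a fair trade-off. Stating the basis of 10 and 160 and counting the excluded readings would help a reader but would not change the conclusion.

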#### 9.3.2.2 Analysis Method

Absolute change in SwCl from baseline at Week 4:

Analysis of absolute change from baseline in sweat chloride will be based on an MMRM similar to the primary analysis of the primary efficacy variable. The model will include treatment, visit, and treatment-by-visit interaction as fixed effects with continuous baseline ppFEV1, and age at screening ( $< 18$  versus  $\geq 18$  years of age) as covariates.

Absolute change in CFQ-R respiratory domain score from baseline at Week 4:

Analysis of absolute change from baseline in CFQ-R respiratory domain score will be based on an MMRM similar to the primary analysis of the primary efficacy variable. The model will include treatment, visit, and treatment-by-visit interaction as fixed effects with continuous baseline ppFEV1, and age at screening ( $< 18$  versus  $\geq 18$  years of age) as covariates.

To assess the longitudinal profile of the efficacy and pharmacodynamic assessments with repeated measures up to Week 4, the LS mean (SE) of the within-treatment group change from baseline at each post-baseline visit along with the 95% CI will be estimated from the

corresponding MMRM. The LS mean (SE) of the treatment difference between VX-659/TEZ/IVA and TEZ/IVA at each post-baseline visit will be provided along with the corresponding 95% CI and *P* value. The LS mean (SE) at each visit will also be plotted by treatment group. In addition, the post-baseline raw values and the absolute change from baseline at each post-baseline visit up to Week 4 will be summarized descriptively (n, mean, SD, median, minimum, and maximum).

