12.3.3.2 Analysis of Key Secondary Variables

The key secondary variables are:

- **Absolute change in SwCI from baseline at Week 4:** Analysis of this pharmacodynamics (PD) variable will be based on an MMRM model similar to the analysis of the primary efficacy variable. Data obtained from the Day 15 and Week 4 Visits will be included in the model.
- **Absolute change in the CFQ-R respiratory domain score from baseline at Week 4:** Analysis of this domain will be based on an MMRM model similar to the analysis of the primary efficacy variable. Data obtained from the Day 15 and Week 4 Visits will be included in the model.

Details will be provided in the SAP.

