## 4 INTRODUCTION

This statistical analysis plan (SAP) is based on the most recent approved clinical study protocol (CSP), the most recent approved electronic case report form (eCRF), and the most recent approved eCRF completion guidelines.

This SAP (Methods) documents the planned final statistical analyses of efficacy and safety endpoints defined in the VX17-659-103 study protocol. [REDACTED]

The pharmacokinetic (PK) and pharmacodynamic (PD) characteristics of VX-659/TEZ/IVA in the *F508del* homozygous population also will be evaluated in the study. Selected analyses related to sweat chloride will be documented in this SAP, other PK and PD analyses will be documented separately in the clinical pharmacology analysis plan (CPAP) for the study.

The Vertex Biometrics Department will perform the statistical analysis of the efficacy and safety data; SAS (Version 9.4 or higher) will be used to generate all statistical outputs (tables, figures, listings, and datasets). The SAP will be finalized and approved prior to the final clinical database lock and treatment unblinding for the study. Any revisions to the approved SAP will be documented and approved in an amendment to the SAP prior to the clinical database lock for the final analysis. Any changes made to the SAP (Methods) after the clinical database lock has occurred will be documented in the clinical study report for this study.

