## 7.2 Sample Size and Power

The primary efficacy endpoint is the absolute change in ppFEV1 from baseline at Week 4. The primary null hypothesis to be tested is that the mean absolute change in ppFEV1 from baseline at Week 4 is the same for the TC and TEZ/IVA treatment groups. The null hypothesis will be tested at a 2-sided significance level of 0.05.

Assuming a within-group SD of 7 percentage points and a 5% dropout rate at Week 4, a sample size of 50 subjects in each treatment group for a total of 100 subjects will have approximately 93% power to detect a difference of 5.0 percentage points for the mean absolute change in ppFEV1 from baseline at Week 4 between the 2 treatment groups, based on a 2-sided 2-sample *t*-test at a significance level of 0.05 using the PASS software (Version 11.0).

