### **9.2.2 Demographics and Baseline Characteristics**

Demographics and baseline characteristics will be summarized based on the FAS, and presented by treatment group and overall, as applicable.

Demographic data will include the following:

- Age at baseline (in years)

- Sex (female and male)
- Ethnicity (Hispanic or Latino, not Hispanic or Latino, and not collected per local regulations)
- Race (White, Black or African American, Asian, American Indian or Alaska Native, Native Hawaiian or Other Pacific Islander, and not collected per local regulations)
- Geographic region (North America, Europe [including Israel and Australia])

Baseline characteristics will include the following:

- Weight (kg)
- Height (cm)
- BMI (kg/m^2)

Stratification categories will include the following:

- Age at Screening Visit (<18, ≥18 years)
- ppFEV1 at Day -14 (<70, ≥70)

Disease characteristics will include the following:

- ppFEV1 at baseline (<40, ≥ 40 to <70, ≥70 to ≤90, and >90)
- ppFEV1 at baseline (continuous)
- Sweat chloride at baseline (continuous)
- CFQ-R respiratory domain score at baseline (continuous)
- Prior use of dornase alfa before first dose of study drug in the Treatment Period (Yes, No)
- Prior use of azithromycin before first dose of study drug in the Treatment Period (Yes, No)
- Prior use of inhaled antibiotic before first dose of study drug in the Treatment Period (Yes, No)
- Prior use of bronchodilator before first dose of study drug in the Treatment Period (Yes, No)
- Prior use of inhaled bronchodilator before first dose of study drug in the Treatment Period (Yes, No)
- Prior use of inhaled hypertonic saline before first dose of study drug in the Treatment Period (Yes, No)
- Prior use of inhaled corticosteroids before first dose of study drug in the Treatment Period (Yes, No)
- Infection with *Pseudomonas aeruginosa* within 2 years prior to screening (Positive, Negative)

In addition, data listings will also be provided for:

- Informed consent;
- Inclusion/Exclusion criteria violation for subjects with any such violations.

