### **9.3.2.3 Multiplicity Adjustment**

The key secondary endpoints will be formally tested at an alpha of 0.05 when all subjects complete study participation only if the primary endpoint is statistically significant. A hierarchical testing procedure will be used to control the type I error rate for the multiple key secondary endpoints tested at an alpha of 0.05. For a test at any step to be considered statistically significant within the testing hierarchy, it must be statistically significant, and all previous tests (if any) within the hierarchy must be statistically significant at the 0.05 level. The testing order of the key secondary endpoints is as follows:

- Absolute change in SwCl from baseline at Week 4
- Absolute change in CFQ-R respiratory domain score from baseline at Week 4

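### The sweat chloride and CFQ-R models leave out each endpoint's own baseline, so the two key secondary tests are valid but, in most plausible cases, less precise than the same data allow.

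*SAP*

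**What the plan says.** For the primary endpoint, SAP 9.3.1.2 states: "The model will include treatment group, visit, and treatment-by-visit interaction as fixed effects, with continuous baseline ppFEV 1 , and age at screening". Age enters as two groups, split at 18 years.

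SAP 9.3.2.2 calls the sweat chloride and CFQ-R models similar to that analysis and then writes out the covariates for each in the same words: "The model will include treatment, visit, and treatment-by-visit interaction as fixed effects with continuous baseline ppFEV 1 , and age at screening" group. The list still names ppFEV1. Baseline sweat chloride and baseline CFQ-R score are in neither list.

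Protocol 12.3.3.2 is less specific. For CFQ-R it says "Analysis of this domain will be based on an MMRM model similar to the analysis of the primary efficacy variable", uses equivalent words for sweat chloride, and leaves details to the SAP.

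SAP 9.2.2 lists sweat chloride and CFQ-R respiratory domain score at baseline as continuous disease characteristics, so both variables will exist in the analysis data.

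On testing, SAP 9.3.2.3 states: "A hierarchical testing procedure will be used to control the type I error rate for the multiple key secondary endpoints tested". The order is sweat chloride, then CFQ-R, each at 0.05, and only if the primary endpoint is significant.

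**The concern.** When the outcome is change from baseline, the covariate that usually explains most of its variance is the baseline of that same measure. The primary model has it. The secondary models appear to have inherited the primary model's list unchanged, and in that step the own baseline dropped out. The word similar does not bring it back, because the sentence that follows names ppFEV1 for both endpoints. A programmer working from the SAP would omit it.

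These are the only two key secondary tests in the sequence. CFQ-R comes last and is reached only if sweat chloride succeeds. The visible documents state no power for either. A needlessly large standard error lowers the chance of success at each step and widens both reported intervals.

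The inclusion of baseline ppFEV1 is not at issue. Protocol 9.3.1 expects response to depend on ppFEV1, and randomization is stratified on a related earlier value (Day -14). The gap is the covariate left out.

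**Working it through.** **Inputs from the documents.** 50 subjects per arm, 1:1 allocation, 5% dropout, two-sided alpha 0.05; for the primary endpoint only, SD 7 and difference 5.0 (SAP 7.2). Models and covariates are from SAP 9.3.1.2 and 9.3.2.2.

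**Assumed inputs.** The documents give no SD, correlation or effect size for sweat chloride or CFQ-R. Let rho be the baseline-to-Week-4 correlation given the other covariates, and k the Week 4 SD divided by the baseline SD. I take rho from 0.3 to 0.9 and k of 0.8, 1 and 1.25. The two endpoints need not share values.

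**The plan's own figure.** SAP 7.2 states "approximately 93% power to detect a difference of 5.0 percentage points". With 50 × 0.95 = 47.5 per arm, a two-sample t-test (noncentral t) gives 93.1%. The figure is reproduced. It concerns the primary endpoint only.

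**Formula, Week 4 alone.** In units of the baseline variance:

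- Change score without own baseline: residual variance = 1 + k² − 2·rho·k.
- Own baseline added: residual variance = k²(1 − rho²).
- Standard error ratio, omitted over included = √[(1 + k² − 2·rho·k) / (k²(1 − rho²))].

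At k = 1 this reduces to √[2/(1 + rho)]. For example, at rho = 0.5 it is √(2/1.5) = 1.155.

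**Increase in the standard error from omitting own baseline:**

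| rho | k = 0.8 | k = 1 | k = 1.25 |
|---|---|---|---|
| 0.3 | 41% | 24% | 13% |
| 0.5 | 32% | 15% | 6% |
| 0.7 | 26% | 8% | 1% |
| 0.8 | 25% | 5% | 0% |
| 0.9 | 28% | 3% | 3% |

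The zero at k = 1.25, rho = 0.8 is where the slope of Week 4 on baseline, rho·k, equals 1. The change score is then already the optimal adjustment.

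**Chance imbalance is inside these figures.** At rho = 0.5, k = 1 and 50 per arm, the variance of the treatment difference is (2/50) × 1.00 = 0.040 without own baseline and (2/50) × 0.75 = 0.030 with it. The remaining 0.010 = (2/50) × (1 − 0.5)² is the contribution of baseline imbalance. It should not be counted as a second harm.

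**Power, for illustration.** If a test has 80% power as written, its standardized effect is 1.960 + 0.842 = 2.802. With own baseline and k = 1, power is Φ(2.802 × √[2/(1 + rho)] − 1.960): 93.5%, 89.9%, 86.0%, 84.0% and 82.0% at rho 0.3, 0.5, 0.7, 0.8 and 0.9. From a 95% start, the same step gives 96.7% at rho 0.8 and 95.9% at rho 0.9.

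**Validity.** I simulated trials with no treatment effect: 95 subjects, one visit, ppFEV1 and age group in both models, ppFEV1 correlated 0.2 with the endpoint's baseline, 20,000 trials per rho. Type I error was 4.9% to 5.1% without own baseline and 4.8% to 5.2% with it. Mean estimates were within 0.003 SD of zero in both.

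**Day 15.** The planned models also use Day 15. A two-visit simulation (96 subjects, unstructured covariance, 5% of Week 4 values missing at random, Day 15-to-Week 4 correlations of 0.6, 0.7, 0.8 and 0.92) gave standard error increases of about 23%, 14%, 7.5% and 2% at rho 0.3, 0.5, 0.7 and 0.9. Type I error was near 5% for both models. The second visit does not recover the loss.

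**Cost of the covariate.** At 95 subjects, one more parameter raises the standard error by about √(91/90) − 1 = 0.6%.

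**The case against.** The strongest reply is that nothing here is an error. The SAP prespecifies one covariate set for all three tested endpoints, the tests are valid, and no stated precision or power target for sweat chloride or CFQ-R is missed. The gain is also conditional. It is nil where the slope of Week 4 on baseline is 1, and with equal SDs and correlations of 0.8 to 0.9 it is only 3% to 5% on the standard error. If planned power is already very high, the test result would hardly change. All of this stands, and it limits the point to efficiency.

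Three further reservations also stand:

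- A high correlation is better supported for sweat chloride, which averages two arms (SAP 9.3.2.1), than for CFQ-R. The run-in is meant to give a reliable baseline for both, but nothing in the documents fixes the correlation for the last test in the sequence.
- With dropout, validity rests on data being missing at random given the observed data and covariates (SAP 9.3.1.2). The simulations did not let dropout depend on own baseline. If it does, leaving that baseline out makes the assumption harder to defend.
- Part of the SAP after section 9.3.2 is redacted, so a supporting analysis with own baseline may exist. That would not change the two main models, which are visible in full.

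None of this is a reason to keep the omission. The zero-gain case needs a particular slope. Elsewhere the covariate reduces residual variance, against a cost of about 0.6% on the standard error. Narrower intervals are useful even when both tests succeed.

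**Conclusion.** The concern holds. The omission is plain in SAP 9.3.2.2. Its consequence is lost precision and power for the two key secondary tests. It is not bias or type I error inflation, and it does not touch the primary analysis. With equal SDs the loss is 24% on the standard error at correlation 0.3 and falls to 3% at 0.9. Over Week 4 to baseline SD ratios of 0.8 to 1.25, it runs from 41% to nil. These sizes rest on assumed correlations and SD ratios. That the covariate is missing is certain; how much it matters cannot be settled from the documents. The change should be made because it is nearly free, not because the planned tests are unsound.

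**What to change.** In SAP 9.3.2.2, add continuous baseline sweat chloride to the sweat chloride model and continuous baseline CFQ-R respiratory domain score to the CFQ-R model. Keep baseline ppFEV1 and age group in both. Make the change before database lock and unblinding, by the route in SAP section 4: "Any revisions to the approved SAP will be documented and approved in an amendment to the SAP prior to the clinical database lock".

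The cost is one degree of freedom per model. No new data are needed and no subject is lost, because a change score already requires the baseline value. Protocol 12.3.3.2 leaves details to the SAP, so its text need not change.
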